#### 10.1.9 Returns and Reconciliation

The investigator is responsible for keeping accurate records of the clinical supplies, the amount dispensed to and returned by the patients, and the amount remaining at the conclusion of the trial.

Upon completion or termination of the study, all unused and/or partially used investigational products will be destroyed at the site per institutional standards.

# 10.2 Olaparib

### 10.2.1 Agent Accountability

The sponsor/investigator shall take responsibility for and shall take all steps to maintain appropriate records and ensure appropriate supply, storage, handling, distribution, and usage of investigational products in accordance with the protocol and any applicable laws and regulations.

#### 10.2.2 Mode of Action

The mechanism of action for olaparib activity as a single agent has been proposed to involve the trapping of inactivated PARP onto the single-strand breaks preventing their repair and generating a potential block for cellular DNA replication. An important consequence of this is that processing of trapped PARP-DNA complexes and/or the stalling of replication forks, or collapsing of replication forks, is predicted to lead to the generation of the more serious DNA DSBs.

#### 10.2.3 Description

Olaparib is available as 150 mg and 100 mg tablets.

- 150 mg tablets: green to green/grey, oval, bi-convex, film-coated tablet, with debossment 'OP150' on one side and plain on the reverse, are available in:
  - o Bottles of 60 tablets (NDC 0310-0679-60) and
  - o Bottles of 120 tablets (NDC 0310-0679-12).
- 100 mg tablets: yellow to dark yellow, oval, bi-convex, film-coated tablet, with debossment 'OP100' on one side and plain on the reverse, are available in:
  - o Bottles of 60 tablets (NDC 0310-0668-60) and
  - o Bottles of 120 tablets (NDC 0310-0668-12)

# 10.2.4 Preparation

Olaparib is presented for oral administration as a green, film-coated tablet containing 100 mg or 150 mg of drug substance. The 100 mg strength is also available as a yellow, film-coated tablet. Olaparib tablets are supplied in high-density polyethylene (HDPE) bottles containing desiccant. Bottles are secured with a child-resistant closure; induction-sealed membranes provide tamper evidence.

Dosing containers will be supplied to contain sufficient medication for at least 28 days plus coverage, in form of four 32-count bottles for the standard dose, for example. Olaparib will be dispensed to patients on Day 1 and every 28 days thereafter until the patient completes the study, withdraws from the study, or closure of the study.

## **10.2.5 Storage**

Store at  $20^{\circ}$ C to  $25^{\circ}$ C ( $68^{\circ}$ F to  $77^{\circ}$ F), excursions permitted to  $15^{\circ}$ C to  $30^{\circ}$ C ( $59^{\circ}$ F to  $86^{\circ}$ F). Store in original bottle to protect from moisture.

#### 10.2.6 Route of Administration

Olaparib will be administered orally every 12 hours without regard to food at the dose specified. 100mg and 150mg tablets will be supplied.

## 10.2.7 Patient Care Implications

Expected adverse events and potential risks are described in **Section 7.9.** Appropriate dose modifications are described in **Section 8.2.** No investigational or commercial agents or therapies other than those described below may be administered with the intent to treat the patient's malignancy. If yomiting occurs shortly after the planarib tablets are swallowed, the dose should

If vomiting occurs shortly after the olaparib tablets are swallowed, the dose should only be replaced if all of the intact tablets can be seen and counted. Should any patient enrolled on the study miss a scheduled dose for whatever reason (e.g., as a result of forgetting to take the tablets or vomiting), the patient will be allowed to take the scheduled dose up to a maximum of 2 hours after the scheduled dose time. If greater than 2 hours after the scheduled dose time, the missed dose is not taken and the patient should take their allotted dose at the next scheduled time.

#### 10.2.8 Returns and Reconciliation

The investigator is responsible for keeping accurate records of the clinical supplies, the amount dispensed to and returned by the patients, and the amount remaining at the conclusion of the trial.

Upon completion or termination of the study, all unused and/or partially used investigational products will be destroyed at the site per institutional standards.

# 11.0 CORRELATIVE/SPECIAL STUDIES

Complete instructions for the collection, processing, and shipment of correlative samples will be provided in a separate laboratory manual. All specimens should be correctly labeled with patient initials, study-specific ID number, protocol number, and date of collection.

### 11.1 Tumor Tissue Studies

Tumor tissue samples will be submitted for whole exome sequencing to identify mutations (or liquid biopsy prior to study entry). Detailed instructions for tissue collection, processing and shipment are provided in the laboratory manual. FFPE block and 1 H&E side will be sent to [name] lab for processing. Tumor tissue on slides are optimally  $25 \text{mm}^2$  in area and 4-5 microns thick. For optional on study biopsy see  $\gamma$ H2AX discussion (Section 11.2.2).

# 11.2 Peripheral Blood Studies

Blood for measuring circulating tumor DNA (ctDNA), circulating tumor cells (CTCs), and  $\gamma$ H2AX in CTCS at C1D1 (pre-infusion), C1D8 (pre-infusion), 4 weeks (C2D1) post infusion, 12 weeks (C4D1) post infusion, and at EOT – see study calendar for details. Baseline sample at screening should be collected before patient receives study drug. Complete instructions for the collection, processing, and shipment of samples will be provided in a separate lab manual.

### 11.2.1 Circulating tumor DNA (ctDNA)

Circulating tumor DNA (ctDNA) can be found in the blood of cancer patients, including prostate cancer patients, as part of "liquid biopsy" efforts. There is evidence that ctDNA has value in diagnosis and/or therapeutic applications, including in guiding use of PARP inhibitors in prostate cancer.

Baseline, 4 week, 12 week, and progression plasma samples will be collected in order to evaluate the mutational patters as a function of therapeutic intervention, with the potential to identify new mutations after treatment. Plasma will be obtained by phlebotomy. Blood will be collected in tubes provided in kits supplied by Foundation Medicine. Tubes of 10ml of whole blood are optimally collected for this assay. Collected specimens can be stored at room temperature in the collection tubes and sent via overnight shipment to the processing laboratory.

It was recently reported that a Phase II trial (NCT01485861) of mCRPC patients treated with abiraterone +/- ipatasertib demonstrated that "Baseline (BL) ctDNA positively correlated with radiological progression-free survival (fPDS; HR: 1.8 [95% CI 1.3-2.6], p < 0.01); this association with rPFS was maintained in a multivariate cox model with >5 baseline clinical variables (HR: 1.6 [95% CI 1.1-2.4], p=0.011). Patients with a C3D1 reduction in ctDNA had superior rPFS compared to patients with a C3D1 increase in ctDNA (HR: 2 [95% CI 1.3-3.2]; p < 0.01). The rate of ctDNA clearance at C3D1 was higher with Ipastasertib 400mg arm compared to placebo (56.3% versus 24.4%, p < 0.1). We find that changes in ctDNA associated with best confirmed overall response (p=0.024); CR patients had greatest reduction in ctDNA (mean of -23.4%), followed by PR (-16.3%), then SD (-4.1%), and lastly PD patients (-1.3%). Changes in ctDNA levels correlated with SLD changes (rs = 0.289, p = 0.05) and also PSA changes (rs = 0.33, p < 0.01). Changes in ctDNA were associated with rPFS in a multivariate cox analysis that included PSA change (p < 0.01). "41

We hypothesize that we will be able to retrospectively predict which patients will respond to the combination of ascorbate and olaparib. This will be useful in the

assessment of treatment response, including correlation with rPFS, and will potentially identify mechanisms of resistance.

### 11.2.2 yH2AX foci in CTCs and/or FFPE biopsy tissues

Given that pharmacological ascorbate generates ROS which in turn elicits DNA double-strand breaks, and that PARP inhibition leads to diminished capacity to repair DNA damage, an exploratory endpoint to this study will be to evaluate DNA double-strand breaks via immunostaining for  $\gamma H2AX$  foci in CTCs and optional FFPE biopsy tissues. The extent of DNA damage as determined by  $\gamma H2AX$  foci will be correlated with patient response.

Additionally, given that olaparib targets PARP activity, the impact of the combination of pharmacological ascorbate and olaparib on PARP activity will be evaluated as an exploratory endpoint of this study via immunostaining for PAR (the enzymatic output of PARP activity) in CTCs and optional FFPE biopsy tissues. The extended PARP activity as determined by PAR staining will be correlated with patient response. https://www.embopress.org/doi/pdf/10.15252/emmm.201708816

#### 11.3 Urine Studies

Urine for measuring F2-Isoprostanes and 8-OHdG (markers of oxidative stress) will be collected at Screening, 4 weeks (C2D1), 12 weeks (C4D1), and at EOT - see study calendar for details. Baseline sample at screening should be collected before patient receives study drug. Complete instructions for the collection, processing, and shipment of samples will be provided in a separate lab manual.

### 11.3.1 8-oxo-2'-deoxyguanosine

8-hydrozy-2'deoxyguanosine is a form of damaged DNA caused by excess free radicals and is a marker of DNA oxidation which can be measured in the urine. At baseline, men with prostate cancer have an intermediate level of 8-OH-dG detected in urine, which has transiently increased after radiation therapy in a small study of seven men. Urinary levels were shown to be decreased in men who were treated in a trial of antioxidants with selenium-enriched yeast. Serum levels were shown in one study of 32 men with localized prostate cancer to be decreased following dietary intervention with lycopene. Prostatic tissue levels of 8-OHdG were not significantly decreased in a neo-adjuvant trial of 70 men randomized to pomegranate extract or placebo. In our population, we hypothesize 8-OHdG will be increased after being treated with the study intervention, and will correlate with response to treatment.

#### 11.3.2 F2-Isoprostanes

F2-Isoprostanes are prostaglandin like compounds that are produced by the peroxidation of arachidonic acid, which is catalyzed by free radicals and is independent of cyclooxygenase. Urinary measurement gives an accurate measure of in vivo oxidative stress and is considered to be one of the most reliable biomarkers of oxidative stress. Within men with prostate cancer, there have been

cross-sectional associations with lower levels of 8-isoprostane with higher antioxidant intake. The data is mixed on association of isoprostanes and incident prostate cancer with some studies showing a positive association with F2-isoprostane level and risk of incident prostate cancer and others showing no association with urinary F2-isoprostanes and incident prostate cancer. However, the literature suggests this is the most reliable biomarker and warrants further study in our prostate cancer patients.

### 11.4 Genomic Analysis

Prior genomic sequencing will be collected to document any mutations that are germline or somatic.

## 12.0 DATA REPORTING/REGULATORY REQUIREMENTS

Adverse event lists, guidelines, and instructions for AE reporting can be found in **Section 9.0**.

### 12.1 Data Management

All information will be collected on study-specific case report forms (CRFs) in RedCap by study staff. These data will be reviewed for completeness and accuracy by the Principal Investigator.

CRFs will be used to capture study results and data. The study coordinator or other authorized study personnel will transcribe data from source documents onto paper or eCRFs. Before or between visits, the Protocol Chair (or designee) may request copies of the CRFs for preliminary medical review. Once the CRFs are complete and source-verified, the investigator must sign and date all required pages, verifying the accuracy of all data contained within the CRF.

#### Protocol Chair

The Protocol Chair and/or designee is responsible for performing the following tasks:

- Coordinating, developing, submitting, and obtaining approval for the protocol as well as its subsequent amendments.
- Assuring that all participating institutions are using the correct version of the protocol.
- Taking responsibility for the overall conduct of the study at all participating institutions and for monitoring the progress of the study.
- Reviewing and ensuring reporting of SAE
- Reviewing data from all sites.

#### Coordinating Center (Johns Hopkins University)

The Coordinating Center (or its representative) is responsible for performing the following tasks:

- Ensuring that IRB approval has been obtained at each participating site prior to the first subject registration at that site, and maintaining copies of IRB approvals from each site.
- Monitoring subject registration.
- Collecting and compiling data from each site.
- Establishing procedures for documentation, reporting, and submitting of AE's and SAE's to the Protocol Chair, and all applicable parties.

• Facilitating audits by securing selected source documents and research records from participating sites for audit, or by auditing at participating sites.

# **Participating Sites**

Participating sites are responsible for performing the following tasks:

- Following the protocol as written, and the guidelines of Good Clinical Practice (GCP).
- Submitting data to the Coordinating Center.
- Consent subjects promptly and randomize eligible subjects in EDC.
- Providing sufficient experienced clinical and administrative staff and adequate facilities and equipment to conduct a collaborative trial according to the protocol.
- Maintaining regulatory binders on site and providing copies of all required documents to the Coordinating Center.
- Collecting and submitting data according to the schedule specified by the protocol.
- Comply with auditing and monitoring requests

#### 12.2 Safety Meetings

Scheduled meetings will take place weekly, biweekly or monthly depending on patient enrollment, and will include the protocol principal investigator, study coordinator(s), data manager(s), sub-investigators (as appropriate), collaborators (as appropriate), and biostatisticians (as appropriate) involved with the conduct of the protocol. During these meetings matters related to the following will be discussed: safety of protocol participants, validity and integrity of the data, enrollment rate relative to expectation, characteristics of participants, retention of participants, adherence to protocol (potential or real protocol violations), data completeness, and progress of data for objectives.

Monthly teleconferences will be scheduled to include the Coordinating Center and the clinical trial sites. During these meetings, the Coordinating Center and clinical trial sites shall discuss the following: study protocol updates, safety data, enrollment status, and progress of data for objectives.

#### 12.3 Monitoring

The SKCCC Compliance Monitoring Program will provide external monitoring in accordance with SKCCC DSMP (Version 6.0, 02/21/2019). The SMC Subcommittee will determine the level of patient safety risk and level/frequency of monitoring. Data monitoring of this protocol will occur on a regular basis with the frequency dependent on the rate of subject accrual and the progress of the study. Eligibility for all sites will be monitored by the Protocol Chair or authorized representatives of the Coordinating Center. The protocol will be internally monitored by the Principal Investigator at each site. The PI shall internally monitor the progress of the trial, including review and confirmation of all safety/treatment-related outcomes, response assessments, safety reports and/or any related source documentation. Protocol Chair is ultimately responsible for external monitoring of the trial. External monitoring will occur according to the following guidelines:

Participating Site(s): The protocol will be monitored by authorized representatives of the Coordinating Center.

Authorized representatives of the Coordinating Center will conduct remote monitoring of satellite sites to perform audits or inspections, including source data verification. The purpose of these audits or inspections is to systematically and independently examine all trial-related activities and documents to determine whether these activities were conducted and data were recorded, analyzed, and accurately reported according to the protocol, Good Clinical Practice (GCP), and any applicable regulatory requirements.

Additional data and safety monitoring oversight will also be performed by the SKCCC Safety Monitoring Committee (SMC - as defined in the DSMP).

#### 12.4 Populations of Interest

The safety population includes all subjects who received at least one dose of olaparib and IV ascorbic acid study treatment. The safety population will be conducted on the basis of the actual treatment received. All safety outcomes will be assessed using the safety population for analysis.

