# 1.0 SCHEMA

Total Number of Patients: 15

Olaparib is taken 300 mg BID orally

Ascorbate is given 1 g/kg, 2 times per week intravenously (first three doses [over 1.5 weeks]: titrate 0.25 g/kg, 0.5 g/kg, and 0.75 g/kg. Starting with cycle 1 week 2, the dose of Ascorbate will be 1 g/kg as long as this dose is tolerated)

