# 7.1 Study Calendar

Required Studies	Pre-study 	1 cycle = 28 days		EOT 	LONG TERM FU 			
	Screening	C1D1 	C1D8	C1D15 	C1D22 	CnDn 		
Visit Windows (days) 	-28	+/-3	+/-3	+/- 3	+/-3	+/- 3	-28	+/-28
TREATMENT								
Olaparib		X	X	X	X	X		
Ascorbic acid 		X	X	X	X	X		
ELIGIBILITY								
Inclusion/exclusion review	X							
HRR status 	X							
Informed consent	X							
ECG	X							
PHYSICAL								
Medical and Cancer History	X							
Physical Exam, Weight and ECOG 	X	X	X	X	X	X	X	X
Vital Signs 	X	X	X	X	X	X	X	X
AE/Toxicity Notation 		X	X	X	X	X	X	X
Concurrent meds 	X	X	X	X	X	X	X	X
LABORATORY								
Chemistry 	X	X	X	X	X	$X^7$	X	X
Hematology 	X	X				$X^7$	X	X
Urinalysis	X							
INR and PT/APTT 	X							
Urine Creatinine 	X 	X 				X 	X 	
Testosterone	X							
PSA 	X	X				$X^7$	X	X
G6PD 	X							
CORRELATIVE								
Blood Samples 	NA	X 				X 	$X^{10}$	
Urine Samples 	NA	$X^{11}$				$X^{11}$	$X^{11}$	
Optional Biopsy (Encouraged)	X 	N/A				X 		
DISEASE ASSESSMENT								
Radiologic Evaluation/ RECIST 1.1  or PCWG2	X 					X 	X 	
LONG TERM FOLLOW-UP 								X 

- Longer delays to be approved by the study sponsor. IRB approval is required for all eligibility waivers prior to enrollment. The window for the baseline Radiologic Evaluation/RECIST 1.1 is 6 weeks prior to C1D1.
- Each treatment cycle is 4 weeks (28 days). Ascorbic Acid dosing must be 2 times per week except week 1 when Olaparib is giving alone. The first infusion must occur on day 1 of each cycle and the second infusion can occur any other day during the week as long as it is at least 24 hours from the prior infusion.
- Ports are recommended but not mandatory due to the frequency of infusion.
- 4 After screening, physical exams may be limited as indicated by symptoms. ECOG Eastern Cooperative Oncology Group performance status. Physical exam (including vital signs and weight), ECOG status, AE/Toxicity notation and concurrent medication review have a -3 day window of day 1 of the cycle.

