**Table 2: Regimen Description** 

Regimen Description				
Agent	Dose	Route	Schedule	Cycle Length
Olaparib 	300 mg	Oral	Twice daily, days 1-28	28 days (4 weeks)
Ascorbic Acid	1 g/kg 	0.75-1 gram per minute IV 	Twice weekly  First dose on day 1 of the cycle	

- 1. Olaparib: two 150 mg tablets orally, with or without food, twice daily. The tablets are to be swallowed whole (do not chew, dissolve, or open the tablets). Administration should be in accordance with the package insert. $^{34}$
- 2. For a subject weighing 75 kg, the goal dose is 75 grams (1 g/kg), and the titrated dose schedule is  $18.75 \, \text{g}$ ,  $37.5 \, \text{g}$ , and  $56.25 \, \text{g}$  for cycle 1 only. Rounding the calculated doses to 19 g, 38 g, and  $56 \, \text{g}$  is acceptable. Subsequent doses would be 75 g. The maximum allowed dose for patients weighing over  $100 \, \text{kg}$  is  $100 \, \text{g}$ .
- 3. Infusion time is approximate (± 15 minutes) and may need to be adjusted based on patient tolerability. Infusion time is estimated to be between 90-120 minutes.
- 4. The ideal schedule for ascorbic acid is 3-4 days apart for administration. However, ascorbic acid can be safely administered on consecutive days (at least 24 hours apart). The day that ascorbic acid can be administered can be shifted in the event of holidays, inclement weather, and other reasons for clinic closure to even three consecutive days.

Subsequent ascorbic acid infusions may not be given less than 24 hours apart.

Acute reactions will be managed using standard therapy for acute drug reactions as per institutional standard of care.

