# 7.6.2 Ascorbic Acid Administration

For the first cycle, on cycle 1 day 8, collect blood for CTCs and then start Ascorbic Acid. The first three doses of ascorbic acid will be titrated as such: 0.25~g/kg, 0.5~g/kg, 0.75~g/kg in 1000ml of sterile water (not to exceed 500 mL per hour). If tolerated, the subsequent doses will be 1 g/kg. Infusions will be twice a week, and should not be less than 24 hours apart. It is recommended that ascorbic acid be given through a port due to frequency of infusion, but a port is not required.

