# 9.5 Reporting Adverse Events

# **9.5.1 Reporting Adverse Events (AEs) and Serious Adverse Events (SAEs)** All AEs (both expected and unexpected) occurring from the first dose of study drug

All AEs (both expected and unexpected) occurring from the first dose of study drug will be captured on the appropriate study-specific case report forms (CRFs).

All AEs experienced by subjects will be collected and reported from the first dose of the investigational agent, throughout the study, and will be followed for 30 days after last dose of study drug unless related to the investigational agent.

All SAEs (including death) occurring from the first dose study drug, throughout the study, and 30 days after the last dose of study drug or before initiation of a new antineoplastic treatment (whichever comes first) must be reported. All SAEs that the investigator considers related to the study drug occurring after the follow-up periods must be reported.

In addition, all SAEs, regardless of causality to study drug and/or administration device, will be reported promptly to the IND sponsor (e-mail: [contact], [contact] ), and [contact], within 24 hours of recognition of the event (Appendix B). If this falls on a weekend or holiday, an email notification is acceptable but must be followed by an SAE reporting form on the next business day.

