## 13.8 Analysis of Secondary Endpoints

The **safety analysis** will be performed in all subjects receiving combination olaparib and IV ascorbic acid. AE data will be listed individually and incidence of AEs summarized by system organ class and preferred terms within a system organ class for each treatment group. When calculating the incidence of AEs, each AE (based on preferred terminology defined by Medical Dictionary for Regulatory Activities (MedDRA; Version 13.1, or later) will be counted only once for a given subject. In analyses of grade and causality, if the same AE occurs on multiple occasions, the highest grade and strongest relationship to study drug will be assumed. If 2 or more AEs are reported as a unit, the individual terms will be reported as separate experiences. Changes in vital signs, hematology and clinical chemistry parameters from baseline to the end of the study will be examined. Toxicity will be tabulated by type and grade. Toxicities will be characterized according to the CTCAE version 5.0 Treatment-emergent changes from normal to abnormal values in key laboratory parameters will be identified.

Radiographic progression-free survival (**rPFS**) is defined as the number of months from initiation of therapy (cycle 1, day 1) to date of first radiographic progression, death from any cause, or last patient evaluation. Patients must receive at least one dose of olaparib and IV ascorbic acid to be considered evaluable. Radiographic progression will be determined by modified RECIST criteria 1.1 by development of two or more new bone lesions not consistent with tumor flair for prostate cancer working group 2. Patients who have not progressed or died will be censored at the last date they were assessed and deemed progression-free. rPFS will be summarized and six month estimates for rPFS will be reported using the Kaplan-Meier method with 90% confidence intervals.

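### The safety population requires a dose of both drugs, but week 1 is described as olaparib alone, so a treated patient who leaves before the first infusion is missing from the final safety summaries

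*Combined protocol and SAP*

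**What the plan says.** Section 12.4 defines one safety set: "The safety population includes all subjects who received at least one dose of olaparib and IV ascorbic acid study treatment". It then applies that set without exception: "All safety outcomes will be assessed using the safety population for analysis". Section 13.8 agrees, saying that the safety analysis "will be performed in all subjects receiving combination olaparib and IV ascorbic acid". No other safety set is defined.

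On timing, the treatment footnote to the calendar in 7.1 reads: "Ascorbic Acid dosing must be 2 times per week except week 1 when Olaparib is giving alone". Section 7.6.2 reads: "For the first cycle, on cycle 1 day 8, collect blood for CTCs and then start Ascorbic Acid". Under these two places a patient has taken only olaparib for the first seven days.

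Collection of events is wider than the analysis set. Section 9.5.1 states: "All AEs experienced by subjects will be collected and reported from the first dose of the investigational agent".

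Other places do not fit a day-8 start. Table 2 says of ascorbic acid: "First dose on day 1 of the cycle". The calendar grid marks ascorbic acid at C1D1, and section 11.2 lists a pre-infusion blood sample on C1D1. The schema in section 1.0 says: "Starting with cycle 1 week 2, the dose of Ascorbate will be 1 g/kg as long as this dose is tolerated".

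**The concern.** Membership of the safety set is decided by something that happens after treatment has begun. A patient who takes olaparib and is then lost to toxicity or death, or withdraws, before an infusion has been exposed to study treatment but is not counted. The gap can outlast day 7. Section 8.1 withholds ascorbic acid for drug-related creatinine elevation and for grade 3–4 non-haematological toxicity, and allows olaparib to continue meanwhile. A patient whose first infusion is withheld and never given stays outside the set however long he takes olaparib.

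Safety and tolerability is the first secondary objective, and section 4.2.8 says that the two agents have not been combined before in this disease. With 12 to 15 patients, one uncounted patient with an event moves an incidence by about 6 percentage points. Section 13.5 also allows early drop-outs to be replaced, so an excluded patient may be succeeded by one who tolerated week 1. Section 3.0 counts the 15 patients by any dose of study treatment, so the enrolment count and the safety tables can have different denominators.

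**Working it through.** **1. Who is excluded.** The definition rests on no figure, so the sections are set side by side.

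- Entry to the safety set: both drugs received (12.4, 13.8).
- Exposure on days 1–7: olaparib only (7.1 footnote, 7.6.2).
- Events recorded: from first dose (9.5.1).

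A patient whose participation ends on days 1–7, or whose infusion never takes place, has recorded events and no analysis set. A temporary hold followed by an infusion does not exclude him.

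**2. Direction of the bias.** Let x of n patients on both drugs have the event, and y of m olaparib-only patients. The plan reports x/n. All treated patients give (x + y)/(n + m). The plan's rate is the lower one exactly when y/m > x/n.

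**3. Size.** The documents give no week-1 rate, so the counts are assumed: n = 12, x = 2, and each of the m early leavers has the event (y = m). Intervals are exact (Clopper–Pearson) 90%.

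| m | Plan reports | All treated |
|---|---|---|
| 0 | 2/12 = 16.7% | 2/12 = 16.7% |
| 1 | 2/12 = 16.7% (3.0–43.8%) | 3/13 = 23.1% (6.6–49.5%) |
| 2 | 2/12 = 16.7% | 4/14 = 28.6% (10.4–54.0%) |
| 3 | 2/12 = 16.7% | 5/15 = 33.3% (14.2–57.7%) |

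If instead the one early leaver had no event (m = 1, y = 0), all treated gives 2/13 = 15.4%, and the plan's 16.7% is the higher figure.

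**4. How often it could matter.** If each of 15 treated patients has probability q of leaving before an infusion, the chance of at least one is 1 − (1 − q)^15. For assumed q of 2%, 5% and 10% this is 26%, 54% and 79%. One patient is 1/15 = 6.7% of those treated, and two are 2/15 = 13.3%.

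**5. Link to the monitoring rule in 13.6.** With the stated Beta(2,6) prior, k events in N patients give a Beta(2 + k, 6 + N − k) posterior. Enrolment is held when P(risk > 0.30) is 65% or more. This reproduces Table 9 exactly: 2 events at N = 2, 3 at 3–6, 4 at 7–9 and 5 at 10–12. Table 9 stops at 12. Beyond that, 5 events give 0.67 at N = 12 but only 0.61 at N = 13. Six events give 0.77, 0.72 and 0.67 at N = 13, 14 and 15, so the boundary there would be 6.

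**The case against.** **The start of ascorbic acid is not settled.** Table 2, the C1D1 mark in the calendar grid, and the C1D1 pre-infusion sample in 11.2 point to day 1. The schema does not fit a first titration dose on day 8, because full dose could not then be reached in week 2 after three titration doses over 1.5 weeks. If both drugs start together the week-1 gap largely closes. This stands. What remains is the patient who takes olaparib and never has an infusion.

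**The definition could be read loosely**, as any dose of the combined regimen. The reference in 13.8 to subjects receiving the combination supports the both-drugs reading. If any dose was meant, the wording should say so.

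**Week-1 events would not go unseen.** A reader might infer that early toxicity disappears from all safety oversight. The documents do not support that. AE and SAE reporting runs from first dose, the pause for events of special interest in 13.6 covers any patient, and the 13.6 toxicity rule names no population. The gap is in the final summaries.

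**The bias has no fixed sign.** A reader might infer that exclusion can only flatter the regimen. Step 2 shows that it does so only when the excluded patients have the higher event rate. That is plausible for toxicity stops, but not for event-free withdrawals or failed venous access.

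**Early exits may be rare.** In the cited olaparib trial (4.2.6), at a different dose, 3 of 50 patients (6%) stopped for adverse events over the whole trial. This is a fair caution against assuming many in seven days, although exits for other reasons also count.

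**Conclusion.** The point holds for the final safety summaries. As written, 12.4 and 13.8 omit any patient treated with olaparib who never receives an infusion, and omission can be linked to toxicity. In the assumed example, one such patient with an event moves the reported rate from 16.7% to 23.1%, and three move it to 33.3%. With none, the effect is zero. The 90% intervals are wide in every case, so this is a matter of honest description in a small trial and not of a changed formal conclusion.

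It would be tempting to compare such rates with the 30% in 13.6, for example 3/12 (25%) against 4/13 (31%), and say that a limit has been crossed. The documents do not support that. The 30% there concerns grade 3–4 events still above grade 2 after four weeks off drug, and it is judged by posterior probability. For those counts P(risk > 0.30) is 0.28 and 0.42, both below 0.65.

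The conclusion rests on two things: the both-drugs reading of 12.4, and the olaparib-only week in the 7.1 footnote and 7.6.2. The first is well supported by 13.8. The second is contradicted elsewhere, and the size of the gap depends on how that is resolved.

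**What to change.** - In 12.4 and 13.8, define the safety population as every patient who has taken any dose of either study drug.
- Tabulate adverse events overall and in two periods: before the first infusion and from the first infusion onward. Keep the both-drugs set as a supportive table.
- Reconcile the statements on the first ascorbic acid dose in the schema (1.0), the 7.1 grid and footnote, Table 2, 7.6.2 and 11.2.
- State in 13.6 which patients form the N of Table 9.

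The first two changes need a sentence or so in each section and no new data, because events are already collected from first dose. The reported toxicity rate may come out slightly less favourable. The last change has a further cost if the all-treated set is used for N: Tables 9 and 10 must be extended from 12 to 15 patients, with new boundaries (6 events at N = 13–15 under the present prior and threshold) and recomputed operating characteristics.
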